8. Subjects confirmed eligible for implantation by the Screening Committee will be randomized in a 1:1 fashion to either TAVR or SAVR, stratified by site and the need for coronary revascularization during SAVR. Coronary artery bypass graft (CABG) should be conducted during the index procedure. Concomitant percutaneous coronary intervention (PCI)v and TAVR is encouraged; however staging is left to the discretion of the operator. Intervention/repair of the mitral and/or tricuspid valve is only

---

iiiIf a subject has balloon aortic valvuloplasty after their qualifying TTE, they must have repeat TTE to confirm he/she meets criteria for severe aortic stenosis as described in Section 3.3.5.1 prior to submission to the screening committee.

[figure not shown]
iv Anatomical suitability will be confirmed by Medtronic Screening Lab. Information on MDCT procedures and sizing recommendations is provided in Appendix II, Section 4.0.

v Index PCI should be performed at the TAVR implanting center; index PCI operators will be considered investigators.

allowed if deemed necessary during the SAVR procedure, but there must be no intent to do this type of intervention/repair prior to implant.

9. Trial randomization will not be blinded. Once randomization is complete and a treatment arm is assigned, crossover from SAVR to TAVR treatment is not permitted. The sponsor will strictly monitor device dispensation to ensure that only those subjects randomized to the Medtronic TAVR treatment arm receive the Medtronic TAV. Distribution of the subjects within the trial groups will be controlled at the implanting sites by means of central randomization using interactive voice/web randomization service (IXRS). The randomization scheme will be securely stored at the IXRS provider.
10. Implantation should occur within 90 days of Screening Committee approval.
11. Subjects who consent to participate in the LTI study will also follow the LTI sub-study protocol as described in APPENDIX VII: LEAFLET THICKENING/IMMOBILITY SUB-STUDY PROTOCOL

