## 2. Introduction

This Statistical Analysis Plan has been designed to document, before data are analyzed, the rationale for the study design, and the planned analyses that will be included in study reports. This Statistical Analysis Plan (SAP) is developed based on the Transcatheter Aortic Valve Replacement (TAVR) Low Risk Clinical Investigational Plan (CIP).

The purpose of this trial is to evaluate the safety and effectiveness of transcatheter aortic valve replacement (TAVR) in the treatment of symptomatic severe aortic stenosis (AS) in subjects who are determined by the Heart Team to be at low surgical risk. The Low Risk trial is a multicenter, prospective, 1:1 randomized study designed to demonstrate non-inferiority (within an absolute margin of 6%) of TAVR to SAVR, as measured by a composite of all-cause death or disabling stroke rate at 24 months. The planned sample size is 1200 subjects who undergo an attempted study procedure, and the statistical methods are Bayesian. Study success will be evaluated according to an analysis plan that includes two possible interim analyses, as well as a final analysis. The first interim analysis is timed when 850 subjects have had the chance to be followed for 12 months (12 months after the 850th procedure date); a second interim analysis is timed when 1200 subjects have had the chance to be followed for 12 months (12 months after the 1200th procedure date); and the final analysis is timed when all subjects have had the chance to be followed for 24 months (24 months after the last LTI subject’s procedure date).

A study report will be prepared for submission to US Food and Drug Administration (FDA) at the time study success criteria have been met, for the purpose of seeking market approval. After all subjects have completed all protocol-specified follow-up, a final clinical report including updated long-term safety data will be prepared and submitted.

This document is electronically controlled. Printed copies are considered uncontrolled.

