**Table 1. Surgical series supporting all-cause mortality event rate estimate**

Surgical Series	Number in Cohort	24-Month All-cause Mortality K-M Rate
NOTION SAVR cohort 	134	9.8%
3f Pivotal cohort 	405	12.7%
Mosaic sub-analysis 	646	9.9%
Freestyle sub-analysis 	323	13.5%
Simple Weighted Average	1508	11.4%
 Entire cohort leveraged (data on file)  Sub-group analysis excluding subjects <65 years of age, with congenital bicuspid valves or with a purely regurgitant lesion  Sub-group analysis excluding subjects <65 years of age, with congenital bicuspid valves, with a purely regurgitant lesion or with the Freestyle valve implanted as a full-root replacement		

The 24-month event rate estimate for non-fatal disabling stroke of 3% was generated primarily from the CoreValve US Pivotal High Risk Trial SAVR (3.9%) and TAVR (2.0%) cohorts which used event definitions consistent with this trial. Additional sources of data considered include the NOTION SAVR cohort (4.6%) and the Mosaic and Freestyle cohort sub-analyses (which had rates of 2.0% and 2.3% respectively) all of which collected clinical stroke/cerebrovascular accidents.

The incidence of the primary endpoint of all-cause mortality or disabling stroke at 24 months in each treatment group is expected to be 15%, which is based on an assumed rate of all-cause mortality of 12% at 24 months and a non-fatal disabling stroke rate of 3% at 24 months.

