## 6. Statistical Methods

### 6.1. Randomization

Randomization will follow a 1:1 allocation ratio and be stratified by site and need for revascularization, using a blocked randomization scheme with blocks of randomly varying sizes.

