### 6.5. Primary Objective

The primary endpoint of all-cause mortality or disabling stroke at 24 months will be evaluated using the absolute difference of the TAVR rate and the SAVR rate for all-cause mortality or disabling stroke during a fixed follow-up of 24 months. The hypothesis test is designed to show non-inferiority of TAVR to SAVR for the primary endpoint.

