The maximum number of non-inferiority assessments is three (first interim analysis, second interim analysis, final analysis). The maximum number of superiority assessments is two (simultaneous to passing the non-inferiority assessment for the primary endpoint and the hierarchical testing for the secondary endpoints listed in Section 6.9, or at the final analysis in the event that superiority is not established at one of the interim analyses).

The statistical approach for these analyses is Bayesian. The prior distributions for  $\pi_T$  and  $\pi_C$  in these calculations are Beta(1,1). In each analysis (interim or final), any subject with missing 24-month outcome will have that outcome predicted via a Bayesian piecewise exponential survival model that incorporates follow-up to date. Within a treatment group, let a subject's time to event follow a piecewise exponential model whose hazard function  $\lambda(\tau)$  is piecewise constant over the 3 partitioning intervals defined by the cutoff points 0, 30 days, 183 days, and 730 days. The parameters for each of the 3 intervals are assigned diffuse Gamma prior distributions, with mean 1 and variance 100, which at the time of analysis are updated based on observed data, and unobserved 24-month outcomes are predicted with probabilities determined by this model. Combining predicted and observed 24-month outcomes and integrating out the predictive distributions results in a posterior probability of non-inferiority (or superiority) that accounts for missing data as well as the uncertainty in the prediction, and this is the quantity that is compared to  $\Psi$  (or  $\Psi_{\text{SUP}}$ ) to assess non-inferiority (or superiority). This approach is similar to that taken in the SURTAVI trial, though in this case the statistical model underlying the predictions is based on a time-to-event model rather than a set of beta-binomial models. It is also similar to the approach taken in Wilber et al. The thresholds  $\Psi$  and  $\Psi_{\text{SUP}}$  are selected empirically to achieve a type I error rate (under extensive simulation) of at most 0.05 for non-inferiority testing and at most 0.025 for superiority testing.

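### Need for revascularisation is a randomisation stratum but is absent from the primary posterior and the prediction model, which leaves the posterior slightly too wide if the stratum is prognostic

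*SAP*

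**What the plan says.** SAP 6.1: "Randomization will follow a 1:1 allocation ratio and be stratified by site and need for revascularization". Protocol 3.3.8 gives the same factor more precisely: allocation is "stratified by site and the need for coronary revascularization during SAVR". The stratum is therefore fixed before allocation and recorded for every randomised subject.

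SAP 6.5: the primary endpoint "will be evaluated using the absolute difference of the TAVR rate and the SAVR rate for all-cause mortality or disabling stroke" over 24 months, and SAP 2 sets the target as "non-inferiority (within an absolute margin of 6%) of TAVR to SAVR".

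SAP 6.5.2: the priors for the two arm rates "in these calculations are Beta(1,1"). Within a treatment group, a subject is taken to have a "time to event follow a piecewise exponential model whose hazard function" is constant over three intervals, and unobserved 24-month outcomes are predicted from that model. Neither part has a stratum term. The thresholds Psi and Psi_SUP are found by simulation so that type I error is at most 0.05 (non-inferiority) and 0.025 (superiority). Protocol 3.3.3.4.3 places the simulations and the threshold values in separate documents.

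Need for revascularisation reappears only in SAP 6.10, for subgroup differences and a treatment interaction on the primary endpoint. Neither document gives a stratified primary or sensitivity analysis, or a reason for leaving the stratum out.

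**The concern.** Stratified randomisation balances the arms on the stratum, so the part of the outcome variance that lies between strata drops out of the treatment difference. An analysis with one rate per arm still counts that part, so its posterior is wider than the design warrants. The documents give some reason to think the stratum could matter. SAP 6.10 singles it out as a key subgroup, and under Protocol 3.3.8 the index treatment differs by stratum (CABG with SAVR; PCI with TAVR, concomitant or staged).

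A second, smaller issue is balance in the analysed set. Under SAP 6.2.2 the as-treated set omits randomised subjects with no attempted procedure and groups the rest by first attempted procedure. The balance created at randomisation then holds only approximately, and an unstratified difference does not correct for what is lost.

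At stake is a small amount of precision and some protection against chance imbalance, not the validity of the test.

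**Working it through.** **The plan's own figure.** Inputs from SAP 5.1 and 5.2: the incidence "in each treatment group is expected to be 15" per cent, margin 0.06, alpha 0.05, power 85%. The Farrington-Manning constrained rates under the null are 0.1848 and 0.1248, and alpha is taken as one-sided.

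- s0 = sqrt(0.1848 x 0.8152 + 0.1248 x 0.8752) = 0.5098
- s1 = sqrt(2 x 0.15 x 0.85) = 0.5050
- n per arm = [(1.645 x 0.5098 + 1.036 x 0.5050) / 0.06]^2 = 515.2, so 516 per arm and 1032 in total, as stated
- 1032 / 0.94 = 1098, about 1100; adding 100 gives 1200

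The sample size rests on the unstratified variance, as the analysis does. Stratifying could only lower the requirement.

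**How much the posterior is too wide.** Let f be the share needing revascularisation, p1 and p0 the 24-month risks with and without that need, and p = 0.15 their average. With complete data, the unstratified posterior variance of an arm's rate is about p(1-p)/n. With the stratum balanced by design, the sampling variance is about [p(1-p) - f(1-f)(p1-p0)^2]/n. The overstated share of the variance is therefore

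R2 = f(1-f)(p1-p0)^2 / [p(1-p)], with p0 = 0.15/(1 - f + f x RR) and p1 = RR x p0.

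The documents give neither f nor the risk ratio RR. Assumed ranges: f = 0.15-0.25, RR = 1-2.

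| f | RR | p0 | p1 | R2 | R2 x 1200 |
|---|---|---|---|---|---|
| any | 1 | 0.150 | 0.150 | 0 | 0 |
| 0.15 | 1.5 | 0.140 | 0.209 | 0.49% | 6 |
| 0.25 | 1.5 | 0.133 | 0.200 | 0.65% | 8 |
| 0.15 | 2 | 0.130 | 0.261 | 1.70% | 20 |
| 0.25 | 2 | 0.120 | 0.240 | 2.12% | 25 |

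At 600 per arm, the standard error of the difference is sqrt(2 x 0.1275/600) = 0.0206. In the last row it becomes 0.0206 x sqrt(1 - 0.0212) = 0.0204. Only at RR = 3 does R2 reach 4.4-5.8% (f from 0.10 to 0.50).

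**Effect on the decision.** Simulations used a single look, complete 24-month data, Beta(1,1) priors and true rates of 0.21 v 0.15 (null) or 0.15 v 0.15 (alternative).

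- Illustrative fixed threshold of 0.95, RR = 2: type I error is 0.048-0.050 unstratified and 0.051-0.052 stratified. Power at 600 per arm is 89.9-90.0% and 90.4-90.5%.
- Same threshold, f = 0.15, RR = 1.5: type I error is about 0.051 for both, so the small excess over 0.05 does not come from omitting the stratum.
- Both analyses calibrated to 5% with the stratum effect in the simulation: for RR up to 2, power differs by only about 0.1-0.2 points, and the direction depends on the set-up.

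The three-look design with predicted outcomes was not simulated.

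**Imbalance in the as-treated set (illustration).** If the share needing revascularisation differed by 3 points between arms, with risks of 24% and 12%, the unstratified difference would shift by 0.03 x 0.12 = 0.36 points of the 6-point margin. The documents do not indicate how large any imbalance would be.

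**The case against.** The strongest reply is that stratified randomisation has already delivered the benefit. The unstratified difference has essentially the reduced sampling variance; only its stated posterior is wide, and that width acts through a threshold which is itself tuned by simulation. If those simulations include the stratum effect, Psi absorbs nearly all of it. This stands, and it is why the subject-equivalents above measure posterior width rather than subjects lost. Whether the simulations include the stratum cannot be seen in these documents. If they do not, the result is slight conservatism.

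Other points also stand. The exclusion of Syntax scores above 22 and of unprotected left main disease (Protocol 3.3.5.2) may narrow the risk contrast. Stratifying has a price: hazards rise from 3 x 2 = 6 to 12, and at 15% of 600 a cell holds about 90 subjects per arm, where a Beta(1,1) prior carries more weight. Site, the other stratification factor, is also unmodelled, but with up to 100 sites it would be far less practical to include. The interaction test in SAP 6.10 does not answer the point, because it looks for differing treatment effects and leaves the primary posterior unchanged.

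A reader might infer that interim predictions go wrong if the stratum mix changes during accrual. Nothing in the documents points to such a change. Allocation is 1:1 within site and stratum, so a shift would reach both arms and largely cancel in the difference. The prediction also uses each subject's follow-up to date. No size can be given for this effect, and the point does not rest on it.

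**Conclusion.** The mismatch between the stratified randomisation and the unstratified primary model is real and unexplained, and its consequence is small. The posterior variance is overstated by about 0.5-2.1% (about 6-25 of 1200 subjects) if 15-25% of subjects need revascularisation at 1.5-2 times the risk of the others, with a 15% overall event rate. It is not overstated at all if the stratum is not prognostic. Both the share and the risk ratio are assumed.

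A reader might conclude that precision is being given away at no cost, or that the error rate or the 1200 is in doubt. The documents support neither. The omission makes the test slightly conservative at most, the stated 1032 reproduces, and thresholds calibrated with the stratum effect would recover most of the lost power. What remains is a posterior of the correct width and protection against stratum imbalance in the as-treated set: a minor improvement, worth making because it is cheap.

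**What to change.** In SAP 6.5.2, compute the primary posterior within arm by revascularisation stratum. Combine the stratum rates using the pooled stratum shares as weights, and compare the weighted difference with the 6-point margin (and with zero for superiority). Let the piecewise hazard in the prediction model differ by stratum. State the priors for the stratum-level rates and hazards. Set Psi and Psi_SUP by simulating stratified randomisation with this analysis, and say so in the SAP. Keep the unstratified analysis as a prespecified sensitivity analysis. If the primary model is to stay as it is, prespecify the stratified version as the sensitivity analysis and state whether the threshold simulations included the stratum.

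Cost: SAP wording, additional priors in smaller cells and a re-run of the threshold simulations. No new data are needed, since the stratum is recorded at randomisation.

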### 6.5.3. Note on Timing of Stroke Determination

It may take up to 90 days after a stroke is reported to determine whether it is a disabling stroke. In such cases, the date of the stroke is the date of occurrence and not the date of determination. Furthermore, when the database is locked for interim and final analyses, it is possible that some strokes will still be waiting for the 90-day MRS. In such cases,

This document is electronically controlled. Printed copies are considered uncontrolled.

**Confidential**

the CEC will make their adjudications based on all available data, and the analysis will be based on the CEC adjudicated results.

## 6.6. Description of Performed Analysis, per Population

The primary analysis for the primary endpoint will be performed on the AT set. In addition, it will also be performed on the ITT, Implanted, and PP sets. The inferential statistics for the following secondary endpoints will be performed on the AT set:

- The rate of the composite of death, disabling stroke, life-threatening bleed, major vascular complications, or AKI (II or III) at 30 days
- The rate of new permanent pacemaker implantation at 30 days
- The rate of prosthetic valve endocarditis at one year
- The rate of prosthetic valve thrombosis at one year
- The rate of all stroke (disabling and non-disabling) at one year
- The rate of life-threatening bleeding at one year
- The rate of valve-related dysfunction requiring repeat procedure at one year
- Quality of Life as assessed by Kansas City Cardiomyopathy Questionnaire (KCCQ) at one year
- The rate of repeat hospitalization for aortic valve disease at one year
- New York Heart Association (NYHA) functional classification at 30 days, 6 months, one year, 18 months, 2 years, 3 years, 4 years, 5 years, 7 years and 10 years
- Health-related quality of life at one year as assessed by EQ-5D survey instrument

The implanted set will be used for analyzing the primary endpoint, secondary endpoint of prosthetic valve dysfunction, device success, and echocardiographic assessment of valve performance.

## 6.7. Secondary Safety Endpoints

The following secondary endpoints will be compared between TAVR and SAVR subject cohorts using the appropriate Bayesian version of analysis for comparing proportions. In addition, Kaplan-Meier estimates will be provided.

- The rate of the composite of death, disabling stroke, life-threatening bleed, major vascular complications, or AKI (II or III) at 30 days
- The rate of new permanent pacemaker implantation at 30 days
- The rate of prosthetic valve endocarditis at one year
- The rate of prosthetic valve thrombosis at one year
- The rate of all stroke (disabling and non-disabling) at one year
- The rate of life-threatening bleeding at one year
- The rate of valve-related dysfunction requiring repeat procedure at one year

## 6.8. Secondary Effectiveness Endpoints

- The rate of valve-related dysfunction, defined as moderate or severe prosthetic valve stenosis, or moderate or severe prosthetic regurgitation at one year (per VARC II)

The incidence estimate will be provided for the two treatment groups at the specified time point. The statistical method will be the Bayesian version of a comparison of proportions. The incidence estimates will also be reported at the following time points: 30 days, 6 months, one year, 2 years, 3 years, 4 years, 5 years, 7 years and 10 years.

This document is electronically controlled. Printed copies are considered uncontrolled.

**Confidential**

PROSTHETIC VALVE DYSFUNCTION	
Stenosis: moderate/severe	Any of the following 1) Peak aortic velocity >4 m/s OR mean aortic gradient >40 mmHg, AND EOA <0.8 cm  . 2) Peak aortic velocity >4 m/s OR mean aortic gradient >40 mmHg, AND EOA ≥0.8 cm  , and DVI <0.25, 3) Peak aortic velocity ≤4 m/s and mean aortic gradient ≤ 40 mmHg, AND EOA <0.8 cm  , and DVI <0.25
Paravalvular regurgitation	Moderate/ Severe paravalvular regurgitation
Transvalvular regurgitation	Moderate/ Severe transvalvular regurgitation
Total regurgitation	Moderate/ Severe total regurgitation

## Notes:

1. DVI = Doppler Velocity Index (LVOT VTI/valve VTI)
  2. For subjects with BSA <1.6 m^2, the EOA criteria for significant (moderate or severe) stenosis is <0.6 cm^2
  3. For subjects with LVOT diameter >2.5 cm, the DVI criteria for significant (moderate or severe) stenosis is <0.2 cm^2
  4. Reporting of prosthetic valve dysfunction will be based on core lab results.
  5. Prosthetic valve dysfunction events are not reported as adverse events, unless the dysfunction is accompanied with clinical sequelae at the time of event detection, and the clinical sequelae are chronologically and physiologically associated with the dysfunction. However, prosthetic dysfunctions that are associated with adverse events, and that meet the definition of a serious adverse event, should be reported as such.
- Quality of Life as assessed by Kansas City Cardiomyopathy Questionnaire (KCCQ) at 30 days and one year  
The endpoint will be evaluated using a Bayesian analog of a two-sample t-test. Descriptive statistics for KCCQ change from baseline will also be reported at 30 days, 6 months, one year, and annually through 5 years.
  - The rate of repeat hospitalization for aortic valve disease at one year.  
The incidence estimate will be provided for the two treatment groups at the specified time point. The statistical method will be the Bayesian version of analysis for comparing proportions. In addition, the Kaplan-Meier estimates will be provided at the following time points: 30 days, 6 months, 12 months, 18 months, and annually thereafter through 10 years.
  - Device Success (VARC II), defined as
    - Absence of procedural mortality, AND
    - Correct positioning of a single prosthetic heart valve into the proper anatomical location, AND
    - Intended performance of the prosthetic heart valve, defined as the absence of patient-prosthesis-mismatch and mean aortic valve gradient less than 20 mmHg (or peak velocity < 3 m/sec), AND absence of moderate or severe prosthetic valve regurgitation.

The incidence estimate will be provided for the TAVR group.

The criteria for ECHO will be based on the ECHO Core Lab Data:

- Absence of patient-prosthesis-mismatch
  1. For subjects with BMI < 30 kg/m^2, index effective orifice area (EOAi) > 0.85 cm^2 /m^2
  2. For subjects with BMI ≥ 30 kg/m^2, index effective orifice area (EOAi) > 0.70 cm^2 /m^2
  3. BMI = weight(kg)/(height (m))

This document is electronically controlled. Printed copies are considered uncontrolled.

**Confidential**

- Mean aortic gradient < 20 mmHg or peak velocity < 3 m/sec;
- Absence of moderate or severe prosthetic valve regurgitation. Total Aortic Prosthetic Regurgitation on the ECHO CORE LAB form not equal to moderate or severe.

All of the above components must be satisfied to count as a device success. If any of the above components fails, the endpoint will be counted as a failure.

For the overall device success rate, the numerator will be the number of subjects whose procedures result in device success as described above, and the denominator will be the number of subjects whose device success results are not missing (either success or failure). Note that this analysis excludes those subjects with a missing response to any of the above five components (eg, the field “Post-implant Severity of Total Aortic Regurgitation”=“Unable to Assess” or “Not Recorded”, missing mean aortic gradient, or missing peak velocity, etc.) and without a “NO” response to any of the components.

- Hemodynamic performance metrics by Doppler echocardiography
  - Mean aortic gradient at one year
  - Effective orifice area at one year
  - Degree of total, peri, and transvalvular prosthetic regurgitation at one year

For mean gradient and effective orifice area, the descriptive statistics will be reported at each of the assessed time point (30 days, 6 months, one year, 2 years, 3 years, 4 years, 5 years, 7 years and 10 years). The statistical method will be the Bayesian version of a two-sample t-test.

Prosthetic regurgitation severity will be reported as proportions at each of the assessed time point (30 days, 6 months, one year, 2 years, 3 years, 4 years, 5 years, 7 years and 10 years). The statistical method will be the Bayesian version of a comparison of proportions.

- New York Heart Association (NYHA) functional classification at one year

NYHA function classification will be reported as proportions at each of the assessed time point (30 days, 6 months, one year, 2 years, 3 years, 4 years, 5 years, 7 years and 10 years). The statistical method will be the Bayesian version of a comparison of proportions.

- Health-related quality of life as assessed by EQ-5D survey instrument at one year.

The endpoint will be evaluated using a Bayesian analog of a two-sample t-test.

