### 4.4 Assessment of Prosthetic Aortic Regurgitation

An integrated exam approach using color flow, pulsed-wave (PW), and continuous-wave (CW) Doppler is used to assess the severity of transvalvular and paravalvular aortic regurgitation (AR). Color flow Doppler imaging should be performed from the parasternal long and short-axis views, and the apical long-axis and/or 5-chamber views. In the short axis view, color imaging should be performed at multiple levels (from level of the leaflets to below the skirt and frame to assess paravalvular regurgitation, and at the coaptation point of the leaflets for transvalvular (central) regurgitation).

If AR is seen by color Doppler, a CW Doppler recording of the regurgitant signal should be obtained for measurement of pressure half-time and assessment of jet density. If the degree of AR by color Doppler appears more than mild by visual estimate, the velocity in the proximal descending aorta should be recorded with PW Doppler.

The degree of transvalvular, paravalvular, and total (transvalvular plus paravalvular) AR will be graded as none, trace, mild, mild to moderate, moderate, moderate to severe, and severe based on the synthesis of the Doppler parameters shown in Table 17. The category of “trace” should be used in cases where regurgitation is barely detectable by color Doppler. Regurgitant signals observed to originate within the stent will be considered transvalvular, and regurgitant signals observed to originate outside the stent will be considered paravalvular.

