## 5.0 Core Lab Analysis

Protocol-required echocardiograms will be sent to the Echo Core lab for assessment: the data generated by the Echo Core Lab will be the primary data used for analysis and reporting. Received echocardiograms will be logged in and analyzed by the Echo Core Lab according to their procedures determined for this trial.

The Echo Core Lab will report the following variables:

- Heart rate
- Left ventricular outflow tract (LVOT) diameter in mid systole
- Max aortic/prosthetic valve velocity ( $V_2$ ) by CW Doppler
- Aortic valve velocity time integral (VTI) by CW Doppler
- Mean gradient across aortic valve ( $MGV_2$ ) by CW Doppler
- LVOT VTI by PW Doppler

- Grade of aortic/prosthetic transvalvular regurgitation (post-implant only)
- Grade of aortic/prosthetic paravalvular regurgitation (post-implant only)
- Grade of prosthetic total (transvalvular plus paravalvular) regurgitation (post-implant only)
- Grade of mitral regurgitation
- Grade of tricuspid regurgitation
- Max tricuspid regurgitant (TR) jet velocity (if TR is present)
- Left ventricular internal dimension at end diastole
- Left ventricular internal dimension at end systole
- Interventricular septal thickness at end diastole
- Left ventricular posterior wall thickness at end diastole
- Left atrial diameter (anterior-posterior linear dimension) at systole
- Left ventricular ejection fraction by visual estimate
- Grade of diastolic dysfunction (if present)

Qualitative grading of valvular regurgitation will be performed using the criteria described in Sections 4.4 through 4.7. For reporting the degree of prosthetic regurgitation, the grading classes may be collapsed according to the 3-class grading scheme recommended by the American Society of Echocardiography (ASE)-European Association of Cardiovascular Imaging Guidelines (Table 16).

In addition, the following variables will be derived by the central database from the appropriate measurements reported by the Echo Core Lab:

- **Peak Pressure Gradient (Peak  $\Delta P$ ) Across the Aortic Valve in mmHg**  
Peak  $\Delta P = 4 \times (V_2^2)$   
Where:  $V_2$  is the peak velocity across the prosthesis in m/sec
- **Aortic Valve Area (AVA) in  $\text{cm}^2$**   
AVA = LVOT diameter in  $\text{cm}^2 \times 0.785 \times (VTI_{V1}/VTI_{V2})$   

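### As written, the SAP's device-success rule would pass a core-lab grade of moderate to severe regurgitation if the form carries the protocol's seven-level scale

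*SAP*

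**What the plan says.** SAP Section 6.8 builds device success from several components and takes the echocardiographic ones from the core laboratory: "The criteria for ECHO will be based on the ECHO Core Lab Data". The regurgitation component is first named as "Absence of moderate or severe prosthetic valve regurgitation" and then given an operational rule: "Total Aortic Prosthetic Regurgitation on the ECHO CORE LAB form not equal to moderate or severe". A subject who fails any component is a device-success failure.

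The grades come from the protocol. Under Appendix I Section 4.4, transvalvular, paravalvular and total regurgitation "will be graded as none, trace, mild, mild to moderate, moderate, moderate to severe, and severe". Appendix I Section 5.0 binds the core laboratory to that scale, "Qualitative grading of valvular regurgitation will be performed using the criteria described in Sections 4.4 through 4.7", and lists the total regurgitation grade among the variables it reports. For reporting the degree of prosthetic regurgitation, the same section adds that "the grading classes may be collapsed according to the 3-class grading scheme". Table 17 prints the 3-class row above the finer one, with moderate-to-severe under Moderate and mild-to-moderate under Mild.

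The device-success text in SAP 6.8 does not say which scale the form field carries, does not call for the collapse and does not cite Table 17.

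**The concern.** The rule names two values on a scale that has a third value between them. If the field holds the seven-level grade, moderate to severe is not equal to either named value and the component is met, while the lesser grade, moderate, fails. The rule would then not be ordered by severity, and it would contradict the component it is meant to implement.

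At stake is the TAVR device-success rate, a named secondary effectiveness endpoint. If such a grade appeared in the data, its handling would be settled after the result was known, although the SAP's stated purpose is to fix the analyses beforehand. The independent validation in SAP Section 8 might not catch it: two programmers who both follow the sentence literally would agree with each other.

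**Working it through.** The plan states no figure to reproduce, so the check is an enumeration. Inputs: the seven grades (protocol Appendix I 4.4), the rule (SAP 6.8) and the 3-class row of protocol Table 17. Table 17 has no column for *none*; it is carried through unchanged.

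| Core-lab grade | Rule applied to the seven-level grade | 3-class grade (Table 17) | Rule applied to the 3-class grade |
|---|---|---|---|
| none | met | none | met |
| trace | met | trace | met |
| mild | met | mild | met |
| mild to moderate | met | mild | met |
| moderate | failed | moderate | failed |
| moderate to severe | **met** | moderate | **failed** |
| severe | failed | severe | failed |

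On the seven-level grade, 5 grades meet the component and 2 fail. On the 3-class grade, 4 meet it and 3 fail. The two readings differ in exactly one grade.

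**Direction.** Let *s* of *n* subjects be successes under the 3-class reading. Let *a* be the subjects graded moderate to severe who meet every other component. Let *b* be the subjects so graded who have another component missing and none failed. SAP 6.8 excludes a subject with a missing component unless some component has failed. On the literal reading the *b* subjects therefore leave the denominator, and the rate becomes (*s* + *a*)/(*n* − *b*). This cannot be below *s*/*n*, so any error runs towards a higher rate.

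**Size.** The documents give no frequency for this grade, so *a* and *b* are unknown. With 1200 as-treated subjects and 1:1 allocation, *n* is at most about 1200/2 = 600 in the TAVR arm, and smaller once non-implanted subjects and missing results are removed. With *b* = 0, each subject in *a* adds 1/600 = 0.17 percentage points. Purely as an assumption, if 0.2% to 1% of 600 were affected, that would be 0.002 × 600 = 1.2 to 0.01 × 600 = 6 subjects, or 0.2 to 1 percentage point. Nothing in the documents supports one value in that range over another, and zero is possible.

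**The case against.** The strongest reply is that the sentence is shorthand. A pure string match would also pass a value such as unable to assess, yet the next paragraphs of SAP 6.8 treat unassessable regurgitation as missing. The sentence is therefore not complete program logic, and the component's name shows the intent. The mapping also exists already in Table 17, and the core-lab form is not in the documents. If it offers only collapsed classes, no subject is misclassified.

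Much of this stands. The intent is clear, and an actual misclassification cannot be shown. It does not remove the gap, however. The SAP deals explicitly with unassessable and missing values but not with moderate to severe. The collapse is permissive, is written for reporting, and is not linked to device success. Its cross-reference is also wrong: Appendix I 5.0 points to Table 16, which lists device components, while the grading scheme is in Table 17.

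A reader might also infer that the one-year valve-dysfunction rate is too low, because the SAP's table for that endpoint says only "Moderate/ Severe total regurgitation". The documents do not support this. Protocol Appendix V Section 3.0 defines the regurgitation categories of that endpoint by the 3-grade scheme, the event code list has only moderate and severe codes, and the SAP table contains no inequality test. Under the 3-grade scheme, moderate to severe counts as moderate and is included.

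**Conclusion.** The point holds conditionally. As written, the rule gives the wrong answer for one grade if the core-lab form carries the seven-level scale and the rule is programmed literally. The protocol text supports the first condition, since the core laboratory grades on that scale, but the form itself cannot be checked.

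A reader might infer that the reported TAVR device-success rate is certainly too high. That goes too far: only the direction of a possible error is established, not its occurrence or its size.

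The consequence is limited. SAP 6.8 provides device success as an incidence estimate for the TAVR group only, without a comparison with SAVR. It is not in the ordered list of SAP 6.9 and supports no labeling claim. The primary endpoint and the hierarchical tests are unaffected. The correction is worth making because it is cheap and removes a decision that might otherwise be taken after the data are seen.

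**What to change.** In SAP 6.8, state that the regurgitation component of device success applies to the 3-class grade of total prosthetic regurgitation in protocol Table 17. Spell out the result: moderate, moderate to severe and severe fail the component; none, trace, mild and mild to moderate meet it. This uses the protocol's own mapping and sets no new threshold. When writing the sentence, check the response options on the core-lab form so that the program names every value the field can hold.

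The cost is one sentence in a SAP revision and one programming condition. The reported rate could be slightly lower if any subject has this grade. No change to protocol Appendix I is needed, and none to the valve-dysfunction endpoint.
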